#### 1.2.2 Work-package 2 objectives

The aim of this work-package is to highlight current guidelines for CDI diagnosis and treatment, at both European and national levels, and measure compliance with these. We will also measure the impact of CDI on healthcare systems, and determine if better compliance with guidelines leads to a

lower burden in terms of reducing cases and costs. Objectives and deliverables for WP2 will be closely aligned with those for WP1, using a synergistic approach to study design (see Figure 1). The timing of the objectives has been planned so that data and analyses generated from WP1 will be available for analyses in the required objectives in WP2. In addition, much of the analysis in the cost-effectiveness objective will be based on data generated from earlier objectives within WP2; the timing of these two objectives (O2.5 and 2.6) has therefore been planned accordingly.

Objective 2.1	To highlight current guidelines for disease detection, notification and management/control
Objective 2.2	To determine the heterogeneity in testing density and in following the existing guidance (including identification of missed diagnoses and empiric treatment approach practices)
Objective 2.3	To determine the heterogeneity in current surveillance practices and ways to improve them.
Objective 2.4	To describe current treatment pathways for patients with CDI infection and recurrences.
Objective 2.5	To elucidate the overall costs of CDI, including management of multiples episodes and re-hospitalisation (healthcare perspectives incl. indirect financial impact on the healthcare system).
Objective 2.6	To measure the impact of CDI management on the healthcare system and the impact of current control measures (infection control/antibiotic stewardship).

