#### 3.3.6 Data collection

Data will be collected via a standardised CRF, with a full supporting SOP. The CRF will be completed by the clinical care team at the participating site that submitted the sample (during O1.1). The CRF will not contain any participant identifiable data; all data will be held against a pseudoanonymised study code, with the link back held by the clinical care team only. COMBACTE-CDI investigators will not access participant's notes or access the link back. Once the CRF data has been collected and validated and verified the link-back will be destroyed by the local study site.

Data will be collected on the following variables to examine risk factors for CDI;

- Prior treatment with cytotoxic drugs
- Prior treatment with PPIs
- Underlying diagnoses
- Co-morbidities
- Previous antibiotics (preceding 12 weeks)
- Previous hospitalisation (preceding 12 weeks)
- Admission history (if an in-patient)
- Residential status (if in the community), e.g. home/nursing home
- Previous CDI
- Kissing contact with an infant
- Known contact with CDI case
- Previous wards/movement within hospital

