#### 7.2 Univariate analysis

Univariate analysis will be used to assess outcomes and risk factors; continuous variables will be compared between cases and controls by t-test; categorical variables will be compared between cases and controls by chi-squared (fishers exact where numbers are below 5). Risk ratios (Odds ratio if it is case control study) will be calculated for CDI cases with identified variables of interest. Univariate analysis will be used to assess consistency between countries and between different healthcare settings.

The variables to be included in the univariate analysis are shown in the table in appendix 1.

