#### 7.3 Regression analysis (or Multivariate analysis)

To evaluate risk factors considering confounding, unconditional logistic regression analysis will be perform with case/control as dependent variable, and all variables listed in the univariate analysis as independent variables.

To build the logistic regression model, we will apply a stepwise forward selection to identity risk factors. The process of the forward selection will be recorded to rank the risk factor.

The regression analysis will be performed separately for the three age groups (18-49,50-64 and 65+ years). If there is a reasonable sample size analysis will also be performed for the age group <18 years.

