# Appendix 1. Variable description table

Item	Data Item	Definition	Analysis type	Time window
Number		of variable		
	Study ID			
1. Patient	Demographics	1	Γ	
1.1	Age of patient at time of sample	Continuous	Univariate/multivariate	Patient admission when the sample was taken
1.2	Gender of patient	Binary	Univariate/multivariate	Patient admission when the sample was taken
1.3	Date of sample in COMBACTE	N/A		
1.4	Location of the patient at time of sample	Categorical	Univariate/multivariate	Patient admission when the sample was taken
2. Admissi	on History	1	1	
2.1	If the sample was taken as a hospital inpatient Reason for admission	Categorical	Univariate/multivariate	Patient admission when the sample was taken
2.1.1	Date of admission	Number of days between admission and index sample is Continuous	Univariate/multivariate	Patient admission when the sample was taken
2.1.2	Admitting specialty	Categorical Patient admission when the sample was taken	Univariate/multivariate	Patient admission when the sample was taken
2.2	Did the patient move wards during their admission	Categorical	Univariate/multivariate	Patient admission when the sample was taken
2.2.1	If yes, please complete the table	Number of days between admission and movement is	Univariate/multivariate	Patient admission when the sample was taken

		Continuous		
2.3	If the sample was taken as a hospital inpatient Where was patient	Categorical	Univariate/multivariate	Patient admission when the sample was taken
	admitted from			
2.4	If the sample was taken as a hospital inpatient Where was the patient discharged to	Categorical	Univariate/multivariate	Patient admission when the sample was taken
2.5	If the sample was taken in the community patient Reason for GP appointment	Categorical	Univariate/multivariate	Patient admission when the sample was taken
2.6	Did the patient have contact with a healthcare facility 6 months prior to the sample being taken?	Binary	Univariate/multivariate	Up to 6 months previous to sample
2.6.1	If yes and the visit was >24 hours, please complete the table below	Categorical	Univariate/multivariate	Up to 6 months previous to sample
2.6.2	If yes, because the patient had regular outpatient appointments, please complete the table below Frequency of visits - nature of visits	Categorical	Univariate/multivariate	Up to 6 months previous to sample

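### Hospital use after the sample is compared between cases and controls without adjustment for prior hospital stays, which the CRF already records

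*SAP*

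**What the plan says.** SAP 2.5 makes the outcomes of cases versus controls the first analysis objective. SAP 7.2 gives the method: "Univariate analysis will be used to assess outcomes and risk factors; continuous variables will be compared between cases and controls by t-test". Categorical variables are compared by chi-squared or Fisher's exact test. No covariate is named.

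SAP 7.3 holds the only regression. Its purpose is "To evaluate risk factors considering confounding". Its form is "unconditional logistic regression analysis will be perform with case/control as dependent variable, and all variables listed in the univariate analysis as independent variables", and for building it, "we will apply a stepwise forward selection to identity risk factors".

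Appendix 1 lists these items on hospital use after the sample:
- 10.1 and 10.3: discharge within and after 30 days, with days (inpatients).
- 10.2: readmission within 30 days (inpatients).
- 10.4: admission within 30 days (community patients).
- 10.6: admission between 30 days and 6 months (all patients).

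All are tagged for both univariate and multivariate analysis.

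The same CRF looks backwards. Item 2.6 asks about healthcare contact in the 6 months before the sample. Item 2.6.1 continues: "If yes and the visit was >24 hours, please complete the table below". For inpatients, item 2.1.1 gives the timing of the sample within the stay: "Number of days between admission and index sample is Continuous".

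Protocol 3.3.6 includes "Previous hospitalisation (preceding 12 weeks)" among the variables collected to examine risk factors. The informed-consent text in protocol 1.4.2 says that repeated hospital visits, common in elderly patients who lack capacity, put them at higher risk of CDI. SAP section 4 matches controls on location only, that is, site and hospital or community setting.

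**The concern.** A patient who was often in hospital before the sample is likely to be admitted again afterwards, with or without CDI. If cases had more prior stays than controls, an unadjusted comparison of later admissions counts part of that prior difference as a consequence of CDI. The plan looks for exactly such a difference under its second objective (risk factors) but makes no allowance for it under the first (outcomes).

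Matching on site and setting removes only the part of prior use that goes with location. Differences between patients within a site remain. At stake is how any excess of admissions among cases is read: whether it follows CDI, or was already there.

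**Working it through.** **1. Does any planned analysis adjust later hospital use for earlier use?**
- SAP 7.2: outcomes are compared by case status, with no covariate.
- SAP 7.3: the dependent variable is case status. Items 10.x could enter only as predictors of it, which puts events after the sample on the explanatory side. Selection is forward stepwise, so items 2.6 and 2.6.1 may or may not be kept. Days are never a dependent variable, so no adjusted difference in days is produced.
- Nowhere else in the SAP is later hospital use modelled.

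**2. Size for the admission items.** The plan states no figure to reproduce: it gives no admission rate, prior-stay rate or power for these items.

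Inputs from SAP 2.1, Table 1, which are maximum recruitable numbers:
- All patients: 213 cases, 512 controls (item 10.6).
- Hospital: 156 and 365 (item 10.2).
- Community: 57 and 147 (item 10.4).

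Assumed inputs, not in the documents: the share with a prior stay (p) in cases and controls, and the later admission risk with (r1) and without (r0) a prior stay. The risks are the same in cases and controls, so CDI has no effect. The test is two-sided at 5%; SAP section 3 gives 5% without stating sidedness.

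Formulas:
- Crude risk = p × r1 + (1 − p) × r0.
- z = risk difference / SE, with SE = √[A(1−A)/n₁ + B(1−B)/n₂], where A and B are the crude risks in cases and controls.
- False-positive rate = P(Z > 1.96 − z) + P(Z < −1.96 − z).

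Mild scenario (prior stay 45% v 35%; risks 40% and 25%):
- Cases: 0.45 × 0.40 + 0.55 × 0.25 = 0.3175.
- Controls: 0.35 × 0.40 + 0.65 × 0.25 = 0.3025.
- Risk ratio 1.05. At 213 v 512, SE = 0.0378, z = 0.40, rate 6.8%.

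Stronger scenario (prior stay 60% v 40%; risks 50% and 25%):
- Cases: 0.60 × 0.50 + 0.40 × 0.25 = 0.40.
- Controls: 0.40 × 0.50 + 0.60 × 0.25 = 0.35.
- Risk ratio 1.14. At 213 v 512, SE = 0.0396, z = 1.26, rate 24.3%.

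The same two scenarios at the numbers that apply to each item:

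| Item | Cases v controls | Mild | Stronger |
|---|---|---|---|
| 10.6 | 213 v 512 | 6.8% | 24.3% |
| 10.2 | 156 v 365 | 6.3% | 18.9% |
| 10.4 | 57 v 147 | 5.5% | 10.1% |

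With equal prior use, A = B, z = 0 and the rate is 5%: no bias. The spurious risk ratio does not depend on sample size; only its chance of reaching significance does.

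**3. Does adjustment remove it?** A simulation without a CDI effect (1,000 runs per scenario, 213 v 512, risks 40% and 20%) used five assumed pairs of prior-stay shares, from 50% v 50% to 60% v 30%. The crude chi-squared test rejected in 4.1% to 37.5% of runs. A Mantel-Haenszel test stratified by prior stay rejected in 3.7% to 5.1%.

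**4. Days to discharge (10.1, 10.3).** Item 2.1.1 locates the sample within the index stay, and days to discharge is what remains of that stay. The documents give neither the relation between the two nor any case-control difference, so no bias figure is offered for days.

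**The case against.** **The multivariate tag.** Items 10.x and the prior-use items are all tagged for multivariate analysis. For a binary item the conditional odds ratio is roughly the same whichever variable is the dependent one. A 7.3 model that kept both readmission and prior stay would therefore give something close to an adjusted association. This stands as far as it goes: the SAP does contemplate models that could hold both. It is not a remedy, because selection decides whether prior stay is kept, other events after the sample may sit in the same model, and days are never an outcome.

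**Higher prior use in cases is not shown.** Correct. The protocol lists previous hospitalisation as a candidate, gives a direction only for a vulnerable elderly group, and states no case-control figure. Controls also had unformed stools sent to the same laboratories. The imbalance is plausible, not established.

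**These are not the main outcomes.** Also correct. Protocol 3.2.2 makes crude mortality primary and names length of stay, but not readmission, as secondary.

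**Adjustment can remove real burden.** Where prior stays were themselves due to earlier CDI, adjusting for them takes out part of the effect of repeated episodes. This stands and shapes the fix. Age and comorbidity also remain unadjusted, so prior stay closes only one path.

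**Stronger readings that the documents do not support.**
- A reader might take item 2.1.1 as the baseline value of days to discharge, and infer an upward bias in days. It is sample timing. A case admitted with diarrhoea may be sampled early, so the direction is open.
- A reader might conclude that the costing is biased, since the protocol's objective 2.5 is "To elucidate the overall costs of CDI, including management of multiples episodes and re-hospitalisation". Protocol 1.4.2 derives that dataset from objectives 2.1 to 2.4, and protocol 3.5.7 names objective 1.3 data for indirect costs. Section 1.3 says in general terms that all data feed in, but nothing names the crude 7.2 contrast as the cost input.

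**Conclusion.** The point holds in limited form. Hospital use after the sample is compared without adjustment, no planned model takes it as the outcome, and prior stays recorded on the same CRF are not forced into any analysis. The protocol's own reasoning makes confounding by prior use plausible, and location matching does not rule it out.

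The size is unknown. Under the two assumed scenarios the spurious risk ratio for admission is 1.05 or 1.14, and the false-positive rate at the full numbers is about 7% or 24%, lower for the items restricted to inpatients or community patients. These figures rest on assumed prior-stay shares and risks, no CDI effect, and full recruitment. The bias is nil if prior use is equal. No size or direction is claimed for days to discharge. This is a cheap improvement to secondary comparisons; it does not alter the crude mortality outcome.

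**What to change.** Add to SAP 7.2 and 7.3:

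1. **Admission items (10.2, 10.4, 10.6).** Prespecify a model with the admission item as the outcome, case status as the exposure, and any stay over 24 hours in the 6 months before the sample (2.6 and 2.6.1, excluding the index admission) as a fixed covariate outside stepwise selection. Use the number of stays if the CRF table allows; Appendix 1 types 2.6.1 as categorical and does not show the table.
2. **Days to discharge (10.1, 10.3).** Model days with case status as the exposure and days from admission to sample (2.1.1) as a covariate for sample timing.
3. **Reporting.** Give the crude result beside each adjusted one.
4. **Sensitivity analysis.** Repeat without patients who had CDI before the index sample (items 4.1 and 4.6), because their prior stays may be part of the CDI burden.
5. **Section 7.3.** State that items 10.x are outcomes and are not candidate predictors of case status.

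The cost is SAP wording and a few models on data already collected. Two downsides should be stated: patients with a missing covariate leave the adjusted model, and in patients with earlier CDI the adjustment may remove part of the burden. Both are reasons to keep the crude estimate.

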## 2.1 Selection of case and controls (total possible to be recruited)

		Location	of participant a sample	at time of
Diagnostic categories:		Hospital	Community	TOTAL
CDI positive cases	1. CCNA positive	83	20	103
	2. CCNA negative/Simoa positive	49	22	71
	3. CCNA and Simoa negative but CTC positive or bioFire pos	24	15	39
CDI negative controls	4. Negative control *	365	147	512
Total number selected for case/control study 521 204		725		

Table1. The total number of samples selected for the case/control study (n=725). The table shows the number of CDI positive cases according to the indicated diagnostic categories (1-3, n=213) and by location of participant (Hospital n=156, Community n=57). Negative controls (4, n=512) were selected at a rate of 1:3 from matching participating sites (one case to three controls). As some participating sites had less than 3 controls per case, average rate was of 1:2.4 (one case to 2.4 controls) (\*).

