#### 5. Handling of missing values and other data conventions

Where data is unknown, 'data unavailable' will be entered onto the data management system. Patterns of missing data will be described. Where an individual has a missing value for one of the study outcomes, they will be excluded from the analysis of that outcome. Sensitivity analysis can be used to determine the potential effect of missing data.

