## 7. Statistical methodology and statistical analysis

#### 7.1 Descriptive analysis

Distribution of demographic, concomitant pathogens, medical conditions, medical procedures, and medication used will be tabulated by case and controls. The analysis will also be stratified by age group (<18, 18-49 years, 50+ 50-64 years, 65 +, 65--84 years, and 85 + years).

Where data are continuous variables, means and standard deviations will be presented; where these data have a highly skewed distribution, medians, 25th and 75th percentiles will be presented. Where data are categorical variables, the number and percentage of participants within each category will be presented. The percentage of missing values will be reported for each variable (continuous or categorical).

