10.3	If the sample was	Binary	Univariate/multivariate	Up to six months		
	taken as a hospital	-		after the index		
	inpatient, was the			sample		
	patient discharged	Continuous	Univariate/multivariate			
	>30 days after the	(no. of				
	sample	days)				
If the sam	ple was taken as a con	nmunity				
patient	•	-				
10.4	Was the patient	Binary	Univariate/multivariate	Up to 30 days		
	admitted to			after the index		
	hospital			sample		
10.4.1	If yes, please give	Continuous	Univariate/multivariate	Up to 30 days		
	dates of the	(no. of		after the index		
	subsequent	days)		sample		
	hospital admissions					
If the sam	If the sample was taken as a hospital inpatient or a community patient					
10.5	Did the patient die	Binary	Univariate/multivariate	Up to 30 days		
	in the 30 days after			after the index		
	the sample			sample		
		Continuous	Univariate/multivariate			
		(no. of				
		days)				
10.5.1	If yes, was the	Binary	Univariate/multivariate	Up to 30 days		
	death linked to CDI			after the index		
				sample		
10.6	Was the patient	Binary	Univariate/multivariate	Up to six months		
	admitted to			after the index		
	hospital between			sample		
	30 days and 6					
	months after the					
	sample					
10.6.1	If yes, please give	Continuous	Univariate/multivariate	Up to six months		
	the dates of	(no. of		after the index		
	hospital admissions	days)		sample		
10.7	Did the patient die	Binary	Univariate/multivariate	Up to six months		
	between 30 days			after the index		
	and 6 months after			sample		
	sample?	Continuous	Univariate/multivariate			
		(no. of				
		days)				
10.7.1	If yes, was the	Binary	Univariate/multivariate	Up to six months		
	death linked to CDI			after the index		

		sample

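### Length of stay is a protocol secondary outcome, but the SAP only offers days to discharge cut at day 30; combine items 10.1 and 10.3 into one time to live discharge

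*SAP*

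**What the plan says.** Protocol 3.2.2 lists patient length of stay among the secondary outcomes of the outcomes case-control study, and 3.2.6 lists it again as a data item. The SAP never uses the term. Appendix 1 carries it in three pieces:

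- item 2.1.1, before the sample: "Number of days between admission and index sample is Continuous";
- item 10.1, hospital inpatients: discharged in the 30 days after the sample, yes/no plus a number of days;
- item 10.3, hospital inpatients: discharged ">30 days after the" sample, yes/no plus a number of days, followed to six months.

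On which variables are tested, SAP 7.2 states: "The variables to be included in the univariate analysis are shown in the table in appendix 1". On how, it states that "continuous variables will be compared between cases and controls by t-test"; categorical variables get chi-squared or Fisher's exact test. SAP 7.1 adds that "where these data have a highly skewed distribution, medians, 25th and 75th percentiles will be presented", but as description only. SAP 7.3 models case status, with "all variables listed in the univariate analysis as independent variables". Days to discharge can therefore enter that model only as a predictor. In-hospital death is recorded separately with a day count (10.5 and 10.7). No text joins 10.1 and 10.3, or says how a death in hospital or a continuing admission is treated.

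**The concern.** Both day counts are conditional on the outcome. Item 10.1 has a value only for a patient discharged alive by day 30, and item 10.3 only for one discharged alive later. If cases stay longer, some of them move out of the first group into the second. The first comparison loses the patients who carry the effect, and the second compares two small groups of long stayers. Neither answers how much longer cases stay in hospital after the sample.

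The yes/no part of 10.1 does carry information on long stay, but not a duration. If a death in hospital is recorded as not discharged, it also mixes death with stay. At stake is a named secondary outcome: its comparison would be weak or misleading, and the handling of deaths and continuing admissions would be settled after the data are seen.

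**Working it through.** **Inputs from the documents.** SAP Table 1 splits the cases "by location of participant (Hospital n=156, Community n=57"). The hospital cases by class are 83 + 49 + 24 = 156, and there are 365 hospital controls. These are maximum numbers. Follow-up is six months (SAP 6.3). SAP 2.5 compares outcomes for cases of each classification with controls. No mean, SD, effect size or power for length of stay is given, so there is no plan figure to reproduce.

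**Assumptions.** Exponential stay after the sample, mean 10 days in controls and 13 in cases (1.3-fold), no deaths, two-sided 5%.

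**Step 1: what 10.1 estimates.** For an exponential stay with mean m, the mean among those discharged by day 30 is m − 30q/(1 − q), where q = exp(−30/m).

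- Controls: q = 0.0498; 10 − 30 × 0.0498/0.9502 = 8.43 days.
- Cases: q = 0.0995; 13 − 30 × 0.0995/0.9005 = 9.69 days.
- Difference 1.26 days against a true 3.00 days: 1.26/3.00 = 42%.

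**Step 2: what 10.3 has to work with.** About 156 × 0.0995 = 16 cases and 365 × 0.0498 = 18 controls pass day 30. An exponential stay has no memory, so the mean difference in this group happens to be about 3 days. With so few patients, power is only about 8%.

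**Step 3: power, by simulation** (Welch t-test on 10.1 days; log-rank or Cox analysis of the combined time to day 180).

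| Hospital cases v 365 controls | 10.1 days | Combined |
|---|---|---|
| All classes, 156 | 37% | 78% |
| CCNA positive, 83 | 23% | 57% |
| CCNA negative/Simoa positive, 49 | 15% | 39% |
| Third class, 24 | 7% | 22% |

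The 10.1 yes/no comparison has about 57% with all 156 cases pooled.

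**Step 4: other assumed shapes.** Share of the true difference shown by 10.1 days, stay still 1.3-fold longer in cases:

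| Control mean (days) | 5 | 10 | 15 | 20 |
|---|---|---|---|---|
| Exponential | 85% | 42% | 22% | 13% |
| Lognormal (log-SD 1) | 72% | 46% | 32% | 24% |
| Gamma (shape 2) | 98% | 67% | 37% | 22% |
| Weibull (shape 0.7) | 57% | 26% | 15% | 10% |

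**Step 5: with deaths.** Assume a control median stay of 7 to 14 days, Weibull shape 0.8 to 1.0, a death rate giving 8% by day 30 in both groups, and a live-discharge hazard ratio of 0.75. Power with pooled cases is then 12–45% for 10.1 days, 11–28% for 10.3 days and 63–72% combined (deaths kept in the risk set). Now assume equal discharge hazards but three times the death hazard in cases (control median 14 days, 10% 30-day death in controls). The discharged cases look 0.4 and 2.2 days shorter in the two parts, although fewer cases leave alive by day 30 (69% v 74%).

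**Step 6: where the pattern changes.**

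- (a) 90% of patients are discharged before day 30 and stay 3 days longer if they are cases; the other 10% stay 40–100 days in both groups. Then 10.1 shows 3.0 days against a true 0.90 × 3 = 2.7. It does not understate, and its test can beat the combined one.
- (b) Cases differ only in having more stays of 40–100 days (20% v 10%), the rest averaging 10 days. The true difference is 0.10 × (70 − 10) = 6.0 days, yet both day comparisons show about 0 (power 5% and 6%). Here the 10.1 yes/no test has 86% and the combined analysis about 66%.

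With no difference in discharge or death, every test rejects in about 5%.

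**The case against.** The strongest reply is that Appendix 1 describes case report form items and is not an analysis specification. No sentence orders a t-test on 10.1 and 10.3 days separately, none forbids adding them, and protocol 3.2.6 lists length of stay as an item in its own right. That is fair: the two t-tests are inferred from SAP 7.2 together with the table. But no other rule for comparing continuous variables exists, and nothing in the SAP defines the joined variable or the handling of deaths.

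A reader might also infer that SAP 5 expressly drops these patients: "Where an individual has a missing value for one of the study outcomes, they will be excluded from the analysis of that outcome". The text does not clearly reach that far. It deals with unknown data, and a patient discharged on day 12 has no 10.3 value because the item does not apply. The restriction follows from how the items are built, whatever SAP 5 means.

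Three further points stand. The 78% power is for pooled cases, whereas SAP 2.5 compares each class, where even the combined analysis has limited power. A hazard ratio alone gives no stay in days, so it would not fill the gap by itself. And in limits (a) and (b) a test already in the plan can be more powerful than the combined one.

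**Conclusion.** The concern holds as a gap in what is estimated. A named secondary outcome has no analysis in the SAP, and the nearest thing to one is two comparisons, each conditioned on discharge time. That conclusion does not depend on any assumed stay distribution.

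The size does. Under the exponential illustration the 10.1 comparison shows about 42% of the true difference. Over the shapes and means tried, the share runs from 10% to 98%, and limit (a) shows no understatement at all. The documents do not support saying that the effect is always diluted, that power is always lost, or that the false-positive rate is raised. Nor do they support reading the pooled power figures as the power of the comparison by diagnostic class. All stay and death inputs are assumptions.

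**What to change.** Add to the SAP, for hospital inpatients:

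1. Combine 10.1 and 10.3 into one time from sample to first live discharge, followed to six months. Treat in-hospital death (a death day from 10.5 or 10.7 with no earlier discharge day) as a competing event, and censor patients still in hospital at six months. State whether a transfer (item 2.4) counts as discharge.
2. Compare each case classification, and all cases together, with controls on this variable, in place of separate t-tests on 10.1 and 10.3 days.
3. Report cumulative incidence of live discharge with a cause-specific hazard ratio, plus a summary in days: for example median time to discharge, or mean days in hospital up to a fixed horizon.
4. Report days from admission to sample (2.1.1) separately.
5. Keep the 10.1 yes/no comparison as supportive, with deaths shown separately.

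The cost is a few sentences and a little more analysis; all the dates are already collected. The drawback is that the combined test is not the most powerful for every shape of stay.
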